Sample Size Calculation: Using the marginal benefit formula for repeated measures (Vickers),⁴⁰ and assuming an average within-person correlation between repeated measurements of 0.5, a sample size of 48/group will give us 80% power to detect an effect size as low as $d=0.62$ for the group main effect (Hypotheses 1a and 1b). Thus, if the average VAS rating in the controls is 3 (± 2 SD), we will be able to detect a VAS rating of 4.24 in migraineurs; smaller differences are unlikely to have clinical significance. For hypothesis 1c, 98 participants will also give us 84% power to detect a bivariate correlation of at least 0.4 between pain catastrophizing scores or emotional reactivity scores and pain unpleasantness levels ($r \leq 0.4$ not likely of clinical significance).

Outcomes

Stimulus-response curves will be generated for each subject using the logarithmic equation: $\log(\text{VAS pain ratings}) = \log(t - 35) * \text{coefficient} + \text{intercept}$ where t represents stimulus temperature.¹ The coefficient and intercept generated for heat pain intensity and heat pain unpleasantness will both be used as outcome variables, as well as scores from the PCS and the DERS.

Data Analyses

Statistical Analyses: We will use mixed effects hierarchical regression models with a distribution and link function appropriate to the outcome (e.g., the best fitting distribution as defined by model selection). Repeated measures within each participant (i.e., experimental trials within a session) will be handled using subject-level random effects. We do not expect missing data for this Aim, given the controlled nature of the experimental session and electronic data capture. The specific analyses are outlined for each hypothesis:

Analyses 1a: We will separately regress the individual pain outcomes (pain intensity, pain unpleasantness) on the factorial effects for group (migraine, control), stimulus (43, 45, 47, and 49 C), and repeated experimental block (1, 2, and 3). Absent any higher order two-way (e.g., group x stimulus) or three-way (e.g., group x stimulus x block) interaction involving group, we will interpret a statistically significant group main effect as evidence that the two groups differ in their experimental pain reports.

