Affective components of pain may be targeted in ways that do not involve medication, which is highly desirable in a condition that is persistent throughout a lifetime and principally affects women of childbearing potential. Research has demonstrated that meditation, a non-pharmacological intervention, differentially decreases the affective over sensory responses to experimental pain in healthy controls. After learning to meditate, one's experience of pain is altered, with diminished affective responses to pain. We will be able to evaluate this effect in the clinical pain condition of migraine by determining if a meditation intervention taught to migraineurs differentially decreases the affective responses over the sensory responses to experimental pain. This work will be a novel contribution that demonstrates the specific mechanisms of meditation-induced pain relief in migraine patients. In summary, distinguishing the sensory from affective components of pain in our research will help us determine if QST measurements can be used as a target for treatment. This ultimately will help us further understand the mechanisms of meditation induced pain relief and allow for more precise, targeted treatment options.

Further, medications alone rarely target the affective/cognitive processes that often play a major role in migraine pain and disability. Because of this high affective/cognitive burden of migraine pain, we hypothesize that therapies that target these factors may be especially beneficial and may differentially impact the affective component of migraine pain. For example, cognitive behavioral therapy (CBT) is efficacious (with Grade A evidence) for migraine prevention.⁶⁷⁻⁷⁰

Mindfulness-Based Stress Reduction (MBSR) has beneficial effects on many health outcomes, including chronic pain conditions.^{42-49,71-74} MBSR is a standardized course in mindfulness meditation and yoga.⁷⁵ Mindfulness meditation involves both 1) focused attention on a sensation like the breath while non-judgmentally disengaging from distracting thoughts; and 2) open monitoring, with non-reactive present-moment awareness of sensory stimuli.⁷⁶ These practices

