No previous studies have used experimental pain to evaluate mechanisms of meditation on migraine. Measures of pain intensity and pain unpleasantness will assess nociceptive processing distinct from clinical pain status, providing a means to determine if clinical pain is differentially susceptible to reduction by MBSR. Further, employing experimental pain methodologies will allow us to distinguish affective from sensory processing, allowing us to test our hypotheses that MBSR reduces the affective more than the sensory experience, and this effect will be greater among patients with a greater affective component to their pain.

We will be able to determine predictors of MBSR response in migraineurs. Identifying simple and inexpensive ways to evaluate response will allow treatments to be targeted to those most likely to benefit.

PRELIMINARY STUDIES

We conducted several epidemiological studies that showed that many adults with neurological conditions, including headaches, use complementary and alternative medicine, despite a lack of evidence.⁸⁴⁻⁸⁹ Further, in adults with migraines/severe headaches in the US, the mind-body therapies of deep breathing, meditation, and yoga are the most commonly used.⁸⁸ However, there have only been a few prior studies with non-standardized meditation and yoga interventions in migraine.⁹⁰⁻⁹² We conducted 2 randomized controlled trials (RCT) of MBSR that demonstrated the safety, feasibility, and efficacy of MBSR in adults with mild cognitive impairment^{93,94} and migraines.⁵⁸ In 19 adults with migraines randomized to either MBSR (n=10) or usual care (n=9), MBSR demonstrated no adverse events, 0% dropout, excellent adherence (daily meditation average: 34±11 minutes; class average: 6/8 sessions), and promising effect sizes across several outcomes, despite being a pilot trial without adequate power (**Table 4**).⁵⁸ Theme analyses from qualitative interviews revealed that MBSR may also decrease emotional reactivity and improve pain cognitive reappraisal processes (e.g., less pain catastrophizing and more pain acceptance). The methods of this pilot trial⁵⁸ will be applied to this research. The results from this study support future studies with larger sample sizes to evaluate mechanisms.

Table 4: Improvements* in MBSR vs. Control Group after MBSR in Adults with Migraines

Measure	Change in MBSR vs. Control, d^f	95% CI^g	Comment
Headaches			Although underpowered, migraines were:

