Hypothesis 2b: MBSR will differentially affect the secondary outcome of the affective component (pain unpleasantness) of experimental heat pain compared to the education control group.

Hypothesis 2c: MBSR will improve the secondary outcomes of mindfulness, emotion regulation, pain acceptance, pain catastrophizing, and headache-related disability compared to an education control group.

Hypothesis 3A: High levels of baseline pain catastrophizing and emotional reactivity scores and high baseline levels of pain unpleasantness for experimental pain will predict the primary outcome response (migraine frequency) to MBSR.

Hypothesis 3B: Changes in mindfulness after MBSR will be directly associated with improvements in migraine frequency.

Sample Size and Randomization

Sample Size Calculation: For hypothesis 2a, using effect sizes from our pilot trial,⁵⁸ and by analyzing the data with our mixed effects hierarchical regression models, 44 participants/group (n=88) will provide >90% power with $\alpha=0.05$ to detect a difference of 1.3 migraine days/month over the course of the trial (used PASS design) (Hypothesis 2a). Hypothesis 2b has a similar power function as Part I of this study. For hypothesis 3: since hypothesis 3b is the most difficult to evaluate, this RCT is powered on this hypothesis. This calculation assumes a multivariable model examining linear changes with the four predictors (plus intercept and slope). A sample size of 88 participants will give us 80% power with effects as small as $R^2 \geq 6\%$ in the variance of the slopes; smaller predictors are unlikely to be clinically significant.¹⁰¹

Randomization: Once 4-week migraine logs are reviewed by study staff to ensure eligibility, participants will be randomized 1:1 to either MBSR or the education control group, stratified by migraine frequency (low frequency of 4-9 headaches/month or high frequency of 10-20 headaches/month). Treatment assignments will be generated by a permuted blocks method with randomly varying block size and sealed in numbered, opaque envelopes. [name] will generate the randomization (using the statistical SAS program "PROC PLAN" statement) and deliver the envelopes to the PI. Participants in both groups will continue to track their migraines with their daily REDCap logs for the duration of the trial.

Definition of Populations

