As done in prior behavioral headache research,⁶⁹ all participants who attend at least ONE class will be included in the intention-to-treat analyses. This is a modified "intent to treat" analysis that ensures exposure to the independent variable and is used and felt to be very important by behavioral scientists.

Outcomes

Our primary outcome will be change in frequency of migraine days, defined as a calendar day (00:00 to 23:59)¹⁰² when the patient reports 4 or more continuous hours of a moderate to severe headache (rating of 6-10 on 0-10 VAS pain intensity scale) and/or they treated a headache with abortive medication. Participants will track their headaches daily with REDCap logs to

demonstrate frequency, severity (both pain intensity and pain unpleasantness, as trained with QST), medications, and associated migraine symptoms (e.g., photophobia, phonophobia, nausea, vomiting). iPod Touch devices with Pendragon software will be available to those without internet access.

Secondary outcomes include changes in migraine severity (measured by pain intensity and unpleasantness on 0-10 VAS scale), migraine duration (hrs), frequency of headache days, headache duration, headache severity (measured by pain intensity and unpleasantness on 0-10 VAS scale), experimental heat pain intensity and unpleasantness (QST measurements), and changes in scores on validated measures of mindfulness, pain acceptance, pain catastrophizing, emotional reactivity, and headache-related disability compared to an education control group; determine factors that predict MBSR response on migraine pain. A headache day is defined as any day when a participant reports the presence of a headache.

We will also characterize participants before/after the intervention using measures of hope, optimism, quality of life, depression, anxiety, perceived stress, self-efficacy, sleep, fatigue, pain interference, satisfaction with participation in social roles, allodynia, and global health.

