
impacted the daily probability of migraine. This effect size will be indexed by converting the daily probability to headache counts as recommended for clinical trials in headache.¹¹⁸ If necessary we will model change using polynomial trajectories (i.e., growth curves) to better fit the time-course of treatment.

Analysis 2b: To examine this hypothesis, we will conduct an ANCOVA with pain unpleasantness at post-treatment as the dependent variable, group as the independent variable, and pain unpleasantness at pre-treatment as the covariate.

Analysis 2c: This analysis is identical to 2b, with the appropriate outcomes.

Analysis 3a: Baseline levels of pain catastrophizing and emotional reactivity will be used as predictors in the multilevel models predicting the trajectory of migraine attacks over the course of treatment.

Analyses 3b: This analysis is similar to 3a, except that changes in mindfulness (i.e., change scores from pre-treatment to post-treatment) will be used as predictor of migraine trajectory.

DATA COLLECTION AND QUALITY ASSURANCE

Data Collection Forms

Information will be collected from REDCap daily headache logs for appropriate diagnosis of migraines during an initial 4 week period prior to randomization and participants will continue to track daily headaches for the duration of the trial. Ipod touches with Pendragon software will be available to those without internet access and unable to use REDCap from home. Experimental heat measurements will be conducted at baseline and at each of the 3 follow-up evaluations. Participants will also complete standardized questionnaires using REDCap at baseline and at each of the 3 follow-up evaluations with an option to complete these questionnaires at home prior to the visit. In addition, a 30 minute qualitative interview will be conducted at the first follow-up visit to evaluate the participants' experience with the interventions. Each interview will be audiotaped. Socio-demographic and clinical information will also be collected at the screening visit.

Description of data that will be recorded on human subjects. Each 30 minute qualitative interview of the migraine and control subjects will be audiotaped and then transcribed. Participants will be photographed one of the study visits. These photos will be stored on the study's secure Ishare. Each subject will have provided informed consent to perform this.

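### Analysis 2b models heat-pain unpleasantness alone, so Part 2 cannot test whether MBSR reduces affective more than sensory pain; in Part 1 the moderation form of hypothesis 1b has no test

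*Combined protocol and SAP*

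**What the plan says.** **Part 2.** The Study Rationale says the work will determine whether "a meditation intervention taught to migraineurs differentially decreases the affective responses over the sensory responses to experimental pain". It adds that experimental pain methods separate affective from sensory processing, "allowing us to test our hypotheses that MBSR reduces the affective more than the sensory experience". The formal hypothesis 2b (Statistical Considerations, General Design Issues) is: "MBSR will differentially affect the secondary outcome of the affective component (pain unpleasantness) of experimental heat pain compared to the education control group". For its test, Data Analyses states: "we will conduct an ANCOVA with pain unpleasantness at post-treatment as the dependent variable, group as the independent variable". Pre-treatment unpleasantness is the covariate.

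Heat-pain intensity is listed with unpleasantness among the secondary outcomes (Part 2, Outcomes). Analysis 2c repeats the 2b model for other outcomes, and hypothesis 2c names them: "MBSR will improve the secondary outcomes of mindfulness, emotion regulation, pain acceptance, pain catastrophizing, and headache-related disability". Intensity is not in that list. On power, the Sample Size section says only: "Hypothesis 2b has a similar power function as Part I of this study".

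**Part 1.** Under Study Objectives and in the Study Rationale, hypothesis 1b is that catastrophizing and emotional reactivity moderate the relation between unpleasantness and intensity. Under Statistical Considerations, hypothesis 1b is instead a migraine-versus-control difference in unpleasantness after adjustment for intensity. Analysis 1b adds intensity to the group model. Analysis 1c enters the two psychological scores as subject-level predictors.

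**The concern.** A claim that one dimension falls more than another concerns a difference between two treatment effects. A model with one dimension as its only outcome cannot estimate that difference. A positive 2b is equally compatible with a selective affective effect, a general analgesic effect, or a general shift in how participants rate pain after training. Separating these is the mechanistic contribution that the Part 2 rationale puts forward.

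An intensity ANCOVA run alongside 2b would not close the gap. Significance on one rating and not on the other is not a test of their difference.

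In Part 1, the moderation hypothesis stated in the objectives would go untested, while a different hypothesis carries its label.

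**Working it through.** **1. Question against model, Part 2.**
- Rationale: the quantity is the MBSR effect on unpleasantness minus the MBSR effect on intensity.
- Analysis 2b: the quantity is the MBSR effect on unpleasantness.
- Analysis 2c: the same model, one outcome at a time, with intensity not among the outcomes of hypothesis 2c.
- General mixed-model text: describes diary entries nested in phases, with no dimension factor for heat pain.

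No planned model contains the first quantity.

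**2. Question against model, Part 1.** Moderation needs intensity × catastrophizing and intensity × reactivity terms. Analysis 1b has intensity but neither score. Analysis 1c has all three as main effects only. The only interactions named (Analyses 1a) involve group with stimulus or block. So the intensity-adjusted version of 1b is tested and the moderation version is not.

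**3. The plan's own power figure.** Part 1 gives 48 per group, d = 0.62, 80% power, "assuming an average within-person correlation between repeated measurements of 0.5". A two-sample t-test at two-sided 0.05 with those inputs has 85% power with no gain from repeated measures. With variance factor (1 + (m−1)×0.5)/m, it has 94% for m = 2 measures and 99% for m = 24. The stated 80% is therefore not reproduced, but it errs on the cautious side and the concern does not rest on it. It describes a group difference on one rating and says nothing about a contrast between two ratings.

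**4. How often 2b is positive when nothing is selective (illustration).** Inputs: n = 44 per group (Part 2, Sample Size); two-sided 0.05; an assumed equal fall d in both ratings relative to control, in SD of one rating; an assumed pre-post correlation ρ.

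Standardized effect = d/√(1−ρ²); noncentrality = effect × √(44/2) = effect × 4.690; df = 85.

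| d | ρ | effect | power of 2b |
|---|---|---|---|
| 0.5 | 0.5 | 0.577 | 76% |
| 0.5 | 0.7 | 0.700 | 90% |
| 0.3 | 0.5 | 0.346 | 36% |
| 0.3 | 0.7 | 0.420 | 50% |
| 0.62 | 0.5 | 0.716 | 91% |

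The last row borrows Part 1's figures, because the plan refers to Part 1 for the power of 2b. In every row the true differential effect is zero.

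**5. The contrast that answers the question.** Take unpleasantness minus intensity after treatment, adjusted for both baseline ratings. Let k be the same-time correlation of the two ratings, with the cross-time, cross-rating correlation taken as ρk. Residual SD = √(2(1−k)(1−ρ²)); df = 84. At zero differential it rejects in 5% of trials. If intensity falls half as much as unpleasantness (0.25 against 0.5 SD), the differential is 0.25 SD:

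| ρ | k | residual SD | power at 0.25 SD | detectable at 80% power |
|---|---|---|---|---|
| 0.5 | 0.6 | 0.775 | 32% | 0.47 SD |
| 0.5 | 0.8 | 0.548 | 56% | 0.33 SD |
| 0.5 | 0.9 | 0.387 | 85% | 0.23 SD |
| 0.7 | 0.6 | 0.639 | 44% | 0.39 SD |
| 0.7 | 0.9 | 0.319 | 95% | 0.19 SD |

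A simulation of an equal 0.5 SD fall (10,000 trials per setting, k = 0.6 and 0.9) agrees. Analysis 2b was significant in 75.8% to 76.1% of trials at ρ = 0.5 and 88.9% to 90.0% at ρ = 0.7. The contrast was significant in 4.6% to 5.3%.

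**The case against.** The formal chain in Part 2 is consistent. The secondary objective is the effect of MBSR on experimental heat pain, hypothesis 2b names the control arm as comparator, and 2b compares the arms. The plan also uses the word differentially for an ordinary between-arm effect in Analysis 2a. One statement in the rationale, that MBSR reduces the affective components of pain, makes no comparison with the sensory side and matches 2b. On this reading, the 76% to 91% is simply correct power to detect a real effect on unpleasantness, not an error rate.

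All of that stands, and it limits the point: 2b is a valid test of its literal hypothesis. It does not remove the gap, because the rationale separately presents the affective-more-than-sensory effect as a hypothesis to be tested, and nothing tests it. The percentages show only how often a positive 2b would occur with no selective effect behind it.

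A reader might also expect 2c to cover intensity. That is arguable, but the hypothesis omits intensity, and separate ANCOVAs would still not test the difference.

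The borrowed inputs transfer poorly. The d of 0.62 is a case-control difference, and the 0.5 is a correlation within a single visit. The calculations are illustrative for that reason, and they do not establish that the contrast would be adequately powered.

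**Conclusion.** The concern holds. Part 2 promises a test of selectivity that no planned analysis provides, and Part 1 states a moderation hypothesis that no planned model contains. Both conclusions follow from the text and need no numerical assumption.

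The size in Part 2 depends on assumed effects and correlations. With an equal fall of 0.3 to 0.62 SD in both ratings, 2b would be positive in 36% to 91% of trials for the combinations tabulated, against about 5% for the proper contrast. The aims affected are secondary and mechanistic, and primary Analysis 2a is untouched. The point should be fixed before analysis, so that the contrast and its scale are not chosen after the results are seen.

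**What to change.** **Part 2.** Either:
- add a group × dimension contrast (unpleasantness against intensity, post-treatment, adjusted for both baseline ratings) as the test of selectivity, state its detectable difference under a stated correlation between the ratings, and keep the unpleasantness ANCOVA as the test of an effect on unpleasantness; or
- reword hypothesis 2b and the rationale as an effect on unpleasantness only, and draw no selective conclusion.

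For the first option, fix two details in advance. One is which heat-pain summary is analysed, since Part 2 does not say whether it is the mean rating or the curve coefficient and intercept used in Part 1. The other is the common scale, since the two VAS ratings have different end labels.

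**Part 1.** Reconcile the two wordings of 1b. If moderation is kept, add intensity × catastrophizing and intensity × reactivity terms to the 1c model. If the moderation is meant to differ between migraineurs and controls, group terms are needed as well, because 1c has none. If moderation is not kept, remove it from the objectives and rationale.

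**Cost.** Text and code only: both ratings are taken after each stimulus, and QST is done at baseline and at every follow-up. The drawback of the contrast is power, 32% to 95% in the example above, and the power statement borrowed from Part 1 does not cover it. Rewording costs no power but gives up the selective claim.
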